7.3.5 Quality of Life

Quality of life (QoL) will be assessed using the Quality of Life Questionnaire for Cancer Subjects (QLQ-C30) (version 3) [8] and the Quality of Life Questionnaire for Myeloma Subjects (QLQ-MY20) [9], [10] developed by the European Organisation for Research and Treatment of Cancer (EORTC).

The QLQ-C30 instrument is a reliable and validated 30-item questionnaire composed of 5 functional scales (physical, role, emotional, social, and cognitive), 3 symptom scales (fatigue, nausea and vomiting, and pain) and a global health status/quality of life scale, and 6 single symptoms (dyspnea, insomnia, appetite loss, constipation, diarrhea, and financial difficulties). The QLQ-MY20 instrument is a 20-item disease-specific modular questionnaire regarding subject-reported symptoms or problems. It is usually completed in addition to the QLQ-C30 questionnaire.

The QLQ-C30 will be scored as described in the EORTC QLQ-C30 Scoring Manual from the EORTC Data Center (2001) [11]. The QLQ-MY 20 will be scored according to the same principles as described in the addendum: scoring instructions for newly validated modules.

A score will be calculated for all scales (categories) shown in Table 4.

Table 4 Scales for Scoring the QLQ-C30 (version 3.0) and QLQ-MY 20

		Number of items	Item Range*	Item numbers (Version 3.0)
QLQ-C30 (Item Numbers 1-30)	Global health status / QoL			
	Global health status/QoL	2	6	29, 30
	Functional scales			
	Physical functioning	5	3	1 to 5
	Role functioning	2	3	6, 7
	Emotional functioning	4	3	21 to 24
	Cognitive functioning	2	3	20, 25
	Social functioning	2	3	26, 27

		Number of items	Item Range*	Item numbers (Version 3.0)
	Symptom scales / items			
	Fatigue	3	3	10, 12, 18
	Nausea and vomiting	2	3	14, 15
	Pain	2	3	9, 19
	Dyspnea	1	3	8
	Insomnia	1	3	11
	Appetite loss	1	3	13
	Constipation	1	3	16
	Diarrhea	1	3	17
	Financial difficulties	1	3	28
QLQ-MY 20 (Item Numbers 31-50)	Functional scales / items			
	Future perspective	3	3	48 – 50
	Body image	1	3	47
	Symptom scales			
	Disease symptoms	6	3	31 –36
	Side effects of treatment	10	3	37 – 46**

*Item range is the difference between the possible maximum and the minimum response to individual items; functional and symptom scales take values from 1 =Not at all to 4= Very Much, resulting in range = 3. Questions regarding global health status take values from 1 to 7, resulting in range =6.

** Question 42 is considered scored “not at all” if question 41 is scored “not at all”.

For all scales (categories), the Raw Score (RS) is the mean of the component items.

In case of missing items within an answered questionnaire, the RS for the scale will only be calculated if at least half of the items from the scale have been answered. In this case the mean will be calculated only including those questions which have been answered.

The RS will be transformed into a standardized score using a linear transformation so that scores range from 0 to 100; a higher standardized score represents a higher ("better") level of functioning for functional scales, or a higher ("worse") level of symptoms for symptom scales. The following formula will be used for transformation:

- Functional scales: $Score = [1 - (RS-1)/range] * 100$
- Symptom scales: $Score = (RS-1)/range * 100$

A global score based upon the sum of all items of the QLQ-C30 and/or the QLQ-MY20 will not be calculated according to the recommendations of the EORTC data center. The Global health status / QoL scale (based on questions 29 and 30) will be used as an overall summary measure for the QLQ-C30.

7.3.6 Exposure

Table 5 shows the variables that will be calculated to measure exposure to study drugs (MOR03087, DEX, LEN, POM). Exposure to MOR03087 will be calculated for all subjects, exposure to LEN and POM will be only calculated for subjects in the respective combination therapy cohorts. Dexamethasone exposure will be derived for subjects in the dose-escalation part

receiving weekly MOR03087 treatment plus dexamethasone, and in subjects in both combination therapy cohorts. In cohorts where dexamethasone may be added later, dexamethasone intake will be summarized within the concomitant medication table.

Table 5 Derived Variables for Exposure

Exposure to Any Study Drug		
Variables calculated on a per-subject basis	Duration of treatment [months]	(date of last dosing day of any IMP – date of first dosing day of any IMP + 1)/██████████
Exposure to MOR03087		
Variables calculated for each study drug administration	Percentage of actual volume administered vs. planned volume [%]	
Actual volume administered [mL]/planned volume [mL]*100%
 
Note: The planned volume is either 100 mL or 250 mL.
 
In case no actual volume administered is given, the value will be set
 
 • to the planned volume in case dosing modified is answered with “No” • to 0 in case dosing modified is answered with “Yes” and the type of modification is “Infusion not given” • to 0 in case infusion page is not filled out, but visit took place, and infusion planned according to treatment schedule and visit date is before last date of dosing • to missing in case dosing modified is answered with “Yes” and type of modification is other than “Infusion not given”. 
In case actual volume is 0 and planned volume is unknown, the percentage will still be calculated as 0%.

	Actual dose administered [mg/kg]	
(Actual volume administered [mL]/planned volume [mL])*Assigned dose [mg/kg]
 
Note: This calculation assumes that the study drug solution is prepared correctly and contains the correct amount of study drug.

	Actual dose administered [mg]	
(Actual volume administered [mL]/planned volume [mL])*Assigned dose [mg/kg]* Weight[kg]
 
Note: Weight will be taken from the same visit from the Vital Signs form. In case no weight is available for this visit the most recent previous available weight will be

		taken.
	Duration of infusion [min]	Duration, calculated as stop time of infusion – start time of infusion
	Duration of infusion [categorized]	Duration will be categorized into: <40min; <1h, <2h; <3h; ≥3h
Variables calculated on a per-subject basis including data of all cycles	Number of cycles initiated	Number of cycles initiated per subject according to the following definition: A cycle will be qualified as “initiated” if at least 1 dose (non null) of study drug was administered in this cycle.
	Number of cycles completed	Number of cycles completed = number of cycles initiated, in case a subject drops out at the end of a cycle (i.e. at Day 22 or later, with last infusion at Day 22 administered in case of weekly treatment), but before start of next cycle. Number of cycles completed = number of cycles initiated – 1, in case a subject drops out within the last cycle.
	Number of cycles with all infusions completed	Number of cycles with all infusions completed (i.e. study drug administration page is filled for all intended infusions of the cycle and it is not ticked “Infusion not given”).)
	Number of infusions administered	Number of all infusions where a study drug administration page is filled and it is not ticked “Infusion not given”.
	Percentage of infusions administered	Number of infusions administered/ Number of planned infusions from Cycle 1, Day 1 up to and including the last visit for which the question “Was treatment modified” was answered (in any form).
	Number of infusions administered with any modification	Number of all infusions with any treatment modification except “Infusion not given”.
	Average percentage of actual volume administered vs. planned volume [%]	Mean of the variable “Percentage of actual volume administered vs. planned volume [%]” over all infusions
	Total actual dose	Sum of the variable “Actual dose

	administered [mg/kg]	administered [mg/kg]" over all infusions
	Total actual dose administered [mg]	Sum of the variable "Actual dose administered [mg]" over all infusions
	Average actual dose administered [mg/kg]	Mean of the variable "Actual dose administered [mg/kg]" over all infusions
	Number of infusions not given	Number of all infusions with "Actual volume administered [mL]" of zero. Missing data will be replaced as described above.
	Percentage of infusions not given [%]	Number of infusions not given / Number of planned infusions from Cycle 1, Day 1 up to and including the last visit for which the question "Was treatment modified" was answered (in any form)
	Shortest infusion duration category per subject	Select from all available infusion duration categories per subject the shortest one in the order of <40min; >=40 min to <1h; >= 1h to <2h; >= 2h to <3h, and ≥3h
Exposure to Lenalidomide		
Variables calculated on a per-subject basis including data of all cycles	Number of days treated	Sum of durations of intake [=Start date – Stop date + 1] over all entries (in the eCRF LEN administration log) with non-zero dose
	Total actual dose taken [mg]	Sum of (durations of intake * dose [mg]) over all entries (in the eCRF LEN administration log)
	Average daily dose taken during days treated [mg/day]	Total actual dose taken [mg]/ Number of days treated
	Average daily dose taken during study [mg/day]	Total actual dose taken [mg]/ Duration of treatment [weeks] *7
	Percentage of actual dose vs. planned dose [%]	Total actual dose taken [mg]/ Planned dose [mg] Where planned dose = sum of (starting dose of each cycle * 21 days), calculated over all cycles initiated. Starting dose of each cycle is taken from eCRF LEN administration page for Day 1 of each cycle

	Number of days with missed doses	Sum of durations of intake of 0 dose [=Start date – Stop date + 1] over all entries (in the eCRF LEN administration log) with reason other than “Subject is in Rest Period between Day22 and Day28”
	Any dose reduction	Any reduced dose applications (compared to starting dose in first cycle)
	Any permanent discontinuation of LEN but continuation of MOR03087	Discontinuation of LEN but continuation of MOR03087 during at least 2 MOR03087 infusions until last MOR03087 dosing day
Exposure to Pomalidomide		
Variables calculated on a per-subject basis including data of all cycles	Number of days treated	Sum of durations of intake [=Start date – Stop date + 1] over all entries (in the eCRF POM administration log) with non-zero dose
	Total actual dose taken [mg]	Sum of (durations of intake * dose [mg]) over all entries (in the eCRF POM administration log)
	Average daily dose taken during days treated [mg/day]	Total actual dose taken [mg]/ Number of days treated
	Average daily dose taken during study [mg/day]	Total actual dose taken [mg]/ Duration of treatment [weeks] *7
	Percentage of actual dose vs. planned dose [%]	Total actual dose taken [mg]/ Planned dose [mg] Where planned dose = sum of (starting dose of each cycle * 21 days), calculated over all cycles initiated. Starting dose of each cycle is taken from eCRF POM administration page for Day 1 of each cycle
	Number of days with missed doses	Sum of durations of intake of zero dose [=Start date – Stop date + 1] over all entries (in the eCRF POM administration log) with reason other than “Subject is in Rest Period between Day22 and Day28”
	Any dose reduction	Any reduced dose (compared to starting dose in first cycle)
	Any permanent	Discontinuation of POM but continuation of

	discontinuation of POM but continuation of MOR03087	MOR03087 during at least 2 MOR03087 infusions until last MOR03087 dosing day
Exposure to Dexamethasone		
Variables calculated on a per-subject basis including data of all cycles	Number of applications	Number of DEX intakes where a study drug administration page is filled and the question “Was dexamethasone taken?” is answered with “Yes”.
	Total actual dose taken [mg]	Sum over all doses administered
	Average actual dose taken during days treated [mg]	Total actual dose taken [mg]/ number of intakes
	Number of infusion days without administration of DEX	Number of all MOR03087 infusions where a study drug administration page is filled out and it is not ticked “Infusion not given” but DEX is not taken
	Any dose reduction	Any reduced dose (compared to starting dose in first cycle)
	Any permanent discontinuation of DEX but continuation of MOR03087	Discontinuation of DEX but continuation of MOR03087 during at least 2 MOR03087 infusions until last MOR03087 dosing day

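### SAP Table 5 gives no value to a planned MOR03087 infusion with neither visit nor page, so average volume and dose can read too high and infusions not given too low

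*SAP*

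**What the plan says.** For each MOR03087 administration, SAP section 7.3.6 (Table 5) derives a percentage of planned volume and a dose. Where no actual volume was entered, four replacement rules apply:

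- dosing not modified: the planned volume is used;
- page marked to show that the infusion was not given: zero is used, whether or not the subject attended;
- blank page: the volume is set "to 0 in case infusion page is not filled out, but visit took place, and infusion planned according to treatment schedule", with the added condition that the visit date falls before the last dosing date;
- any other modification: the volume is set "to missing in case dosing modified is answered with “Yes” and type of modification is other than “Infusion not given".

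The per-subject rows build on these values:

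- Average percentage volume is the "Mean of the variable “Percentage of actual volume administered vs. planned volume [%]” over all infusions"; average mg/kg is formed in the same way.
- Infusions not given are those with a volume of zero, and for that row "Missing data will be replaced as described above".
- Percentage administered is "Number of infusions administered/ Number of planned infusions from Cycle 1, Day 1", and percentage not given is "Number of infusions not given / Number of planned infusions from Cycle 1, Day 1". Both denominators run to the last visit at which the treatment-modification question was answered. An infusion counts as administered if its page is filled and the not-given box is not ticked.
- A cycle has all infusions completed if the "study drug administration page is filled for all intended infusions of the cycle" and none is ticked as not given. Volume is not mentioned.

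Section 10.7 summarises all per-subject exposure variables. Section 7.2 adds pooled tables at the recommended dose.

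**The concern.** The rules cover an attended visit with a blank page and a page marked as not given. They do not cover an infusion for which there was no visit and no page. SAP section 7.1 rules out imputing missing values, so no other provision supplies a zero. Two subjects who miss the same number of infusions are therefore summarised differently according to whether they attended.

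Missed infusions are foreseen: protocol section 8.6 allows delays for medical and other reasons. A subject too unwell to attend is a case these rows ought to show.

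The recommended dosing regimen is a primary endpoint, and the exposure tables are where a reader looks to see whether the regimen could be delivered. For LEN and POM, Table 5 reports actual dose as a percentage of planned dose over all initiated cycles. MOR03087 has no such row, so the two averages are likely to be read as its dose intensity.

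**Working it through.** The plan states no exposure figure, so there is none to reproduce. The check applies the Table 5 rules to a constructed subject.

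**Inputs**

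- Weekly schedule (SAP section 3.1): Days 1, 8, 15 and 22, plus a Day 4 loading dose in Cycle 1. Planned infusions in Cycles 1 to 3 = 5 + 4 + 4 = 13.
- Assigned dose 16 mg/kg.
- Assumed: *m* infusions missed with no visit and no page, before the last visit with the modification question answered; all others given in full.

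**Formulas**

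- Percentage administered = (13 − m)/13.
- Percentage not given, as written = 0/13, because no zero is created. Per planned infusion = m/13.
- Average volume, as written = (13 − m) × 100% / (13 − m) = 100%. Per planned infusion = (13 − m)/13.
- Average dose, as written = 16.0 mg/kg. Per planned infusion = 16 × (13 − m)/13.

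| | m = 1, as written | m = 1, per planned infusion | m = 2, as written | m = 2, per planned infusion |
|---|---|---|---|---|
| Administered | 92.3% | 92.3% | 84.6% | 84.6% |
| Not given | 0% | 7.7% | 0% | 15.4% |
| Sum of the two | 92.3% | 100% | 84.6% | 100% |
| Average volume | 100% | 92.3% | 100% | 84.6% |
| Average mg/kg | 16.0 | 14.77 | 16.0 | 13.54 |
| Total mg/kg | 192 | 192 | 176 | 176 |

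**Same two misses, but the visits took place.** The third rule now supplies two zeros: 11/13 + 2/13 = 100%, average volume 1100/13 = 84.6%, and no distortion. The whole difference comes from attendance.

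**Group level.** SAP section 5 guarantees at least 9 subjects at each recommended dose. If *k* of 9 have *m* such misses, mean percentage volume is overstated by 100 × (k × m)/(9 × 13) points. One subject with one miss gives 100/117 = 0.9 points; three subjects with two misses each give 600/117 = 5.1; all nine with two misses each give 1800/117 = 15.4.

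**Stopped infusions.** Take 12 full infusions and one stopped at half volume.

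- Volume recorded: average volume = 1250/13 = 96.2% and total dose = 16 × 12.5 = 200 mg/kg, both correct.
- Volume not recorded: the fourth rule sets it to missing. Average volume reads 100% instead of 96.2%, but total dose reads 16 × 12 = 192 mg/kg instead of 200, which is too low.

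**The case against.** The strongest reply is that the gap may never open. The second rule gives zero whenever a page is marked as not given, with no condition on attendance. If sites complete that page after a missed visit, every row is right. The eCRF completion rules are not among the documents, so this cannot be excluded. It stands as a limit on size, not as an answer to the rule as written.

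A reader might infer that missed and aborted infusions are hidden throughout and that every distortion flatters delivery. The documents do not support that.

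- Percentage administered divides by planned infusions, so it falls correctly.
- Total dose is unaffected by a no-visit miss.
- A blank page stops its cycle from counting as completed.
- A stopped infusion with a recorded volume enters the averages at its true value. Modified infusions have their own row, and SAP section 10.2 tabulates and lists infusion reactions.
- An unrecorded partial volume can push total dose down.

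Nor do the two percentage rows contradict each other in wording. They fail to add to 100% only under this data pattern and a few similar ones.

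The completed-cycles row is a small matter. Under protocol section 9.1.3, an infusion interrupted for a grade 1 or 2 reaction can be resumed to the full dose. After grade 3 or 4 the subject receives no further study drug, so the cycle normally fails the definition anyway unless the stopped infusion was its last.

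**Conclusion.** The point holds in a limited form. When a visit is missed and no page is filled, average percentage volume and average mg/kg read too high and the number and percentage of infusions not given read too low, while percentage administered is right. In the worked case with two of 13 missed, the error is 15.4 percentage points in volume and in infusions not given, and 16.0 against 13.54 mg/kg. This assumes that pages are left blank after missed visits; the frequency is unknown, and the size is zero if sites mark those infusions as not given.

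It would be wrong to conclude that the recommended dose rests on inflated data. The MTD is determined from DLTs in the DLT Evaluable Population, which has its own minimum-dose rule. The recommended dose follows review of all available safety data and the DMC recommendation (SAP sections 6 and 10.1). Only descriptive exposure tables are affected. The missing volume condition in the completed-cycles row is secondary and mainly a matter of labelling.

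**What to change.** Amend Table 5 as follows.

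1. **Zero rule.** Set volume to 0 for every infusion planned under the subject's actual schedule, up to the last dosing date, that has no infusion page, whether or not the visit took place. Take the schedule after any re-dating of cycles (protocol section 9.1.4) and after any switch to, or agreed exemption from, biweekly dosing (SAP section 3.1). Otherwise delayed cycles and schedule changes would create false zeros. Scheduled dates replace the absent visit dates.
2. **One window.** Define infusions not given as planned minus administered, and use the same end date for the zero rule, both numerators and both denominators. At present the zero rule stops before the last dosing date, while the denominators run to the last visit with the modification question answered. State how pages marked as not given after the last dose are handled, and that a recorded volume of 0 mL is not an administered infusion. The two percentages then sum to 100%.
3. **Completed cycles (minor).** Either rename the row to cycles with all infusions administered, full or partial, or require the full planned volume with a stated tolerance and a rule for volumes set to missing.

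The cost is SAP wording and a small programming change. No new data are needed.

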# 9.1 Investigational Medicinal Products

# 9.1.1 MOR03087

# Laboratory Evaluations prior to each Administration of MOR03087

For all administrations of MOR03087, the following parameters should be taken pre-dose on the day of study drug administration and, if outside the limits described below, administration of MOR03087 should be postponed (see Section 8.6):

Value	Subject should not be dosed with MOR03087 if the value is:
Creatinine	> 3 × ULN
Hemoglobin	< 8.0 g/dL (subject should be transfused before dosing)
Platelets	$< 25.0 \times 10^{9}$ /L (< 30.0 × 10 ⁹ /L in the LEN and POM parts)
WBC	$< 1.0 \times 10^{9}/L$
Potassium	> 6.0 mmol/L
Sodium	> 155 mmol/L
AST/ALT	$> 3 \times ULN$

POM, LEN or DEX might have to be interrupted and/or dose reduced as well according to Section 9.1.4.

MOR03087 is a fully human monoclonal antibody targeting the CD38 membrane protein. It is presented as a clear to slightly opalescent, slightly yellowish sterile solution for injection formulated in a histidine buffer at pH 6.8, with sodium chloride (NaCl) and Tween20. MOR03087 will be provided in a labelled 10R glass vial at a concentration of 8-12 mg/mL with an extractable volume of 5 mL (40 mg/vial-60 mg/vial). The appropriate number of vials will be supplied to each respective site. Four vials will be packed in 1 drug box. MOR03087 must be stored at -20°C  $\pm$  5°C. The drug has to be obtained from the freezer between 3 days to 16 hours before the planned start of the infusion to allow for the preparation of the infusion. The drug has to be thawed as well as stored at 2-8°C until the preparation for infusion. MOR03087 will be diluted in 100 mL or 250 mL as appropriate with commercially available 0.9% NaCl saline (Ecoflac® plus from B. Braun) for injection and will be provided by the sponsor.

The individual MOR03087 infusion will be prepared at the site, according to directions of the sponsor, which will be laid down in a drug preparation manual. It will be administered by slow intravenous (IV) infusion over approximately 2 hours. If any given infusion is well tolerated and could be administered without any infusion reaction, the subsequent infusion should be administered with the next shortest infusion duration according to the following steps: 90 min.,

60 min., 45 min., 30 min. (scheme in Table 3). Infusion duration should not be shorter than 30 minutes.

[figure not shown]

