# Grade 3 or 4 infusion reactions

If a subject presents with grade 3 or grade 4 infusion reactions:

- Infusion should be discontinued immediately.
- Subject should receive appropriate treatment with an H1 antihistamine and/or paracetamol or prednisolone as clinically indicated and, if necessary, further medications (i.e., epinephrine, bronchodilator).
- Subject should not receive further study drug.

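### The shortest-infusion category in SAP Table 5 counts incomplete infusions, and two of its limits sit on the planned 60 and 120 min steps

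*SAP*

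**What the plan says.** SAP 7.3.6, Table 5, builds the variable in three steps.

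- Per infusion, the duration in minutes: "Duration, calculated as stop time of infusion – start time of infusion".
- Per infusion, the category: "Duration will be categorized into: <40min; <1h, <2h; <3h; ≥3h".
- Per subject, the shortest category: "Select from all available infusion duration categories per subject the shortest one". The order starts at under 40 min and goes on ">=40 min to <1h; >= 1h to <2h; >= 2h to <3h, and ≥3h".

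None of these lines mentions the volume given, completion or a reaction. The nearest thing to an admission rule is the definition of an administered infusion in the same table, "Number of all infusions where a study drug administration page is filled and it is not ticked" as not given. A partly given infusion therefore counts. SAP 10.7 then summarises every exposure variable that is calculated per subject.

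Protocol 9.1.1 starts at about 2 hours. After an infusion without a reaction, "the subsequent infusion should be administered with the next shortest infusion duration according to the following steps: 90 min", then 60, 45 and 30 min (Protocol Table 3). For a grade 3 or 4 reaction, Protocol 9.1.3 says "Infusion should be discontinued immediately", and the subject receives no further study drug.

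**The concern.** A minimum is sensitive to a single short record. Here the rule admits two kinds of short record that do not reflect a shorter planned infusion: one that was broken off, and one that ended a minute or so ahead of its planned time at a step where the category limit allows no margin.

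At stake is the meaning of one table. In the SAP text this is the only per-subject variable on infusion duration, so readers will use it to see how far down the shortening scheme subjects went. If a subject taken off drug during the first infusion is counted with those who completed 30 min, the shortest category mixes opposite outcomes.

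**Working it through.** The documents state no result for this variable, so there is no figure to reproduce. The check applies the SAP limits to the protocol steps.

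**Inputs.** Planned steps: 120, 90, 60, 45 and 30 min (Protocol 9.1.1 and Table 3). Category limits: 40, 60, 120 and 180 min, with a value exactly on a limit going to the longer category (SAP Table 5). Timing scatter and frequency of early stops: not given anywhere.

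**Step 1: where the planned steps fall.**

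| Planned step | SAP category at the planned time | Shortfall that changes the category |
|---|---|---|
| 120 min | 2 h to under 3 h | 1 min (119 falls in 1 h to under 2 h) |
| 90 min | 1 h to under 2 h | more than 30 min |
| 60 min | 1 h to under 2 h | 1 min (59 falls in 40 min to under 1 h) |
| 45 min | 40 min to under 1 h | more than 5 min |
| 30 min | under 40 min | none possible |

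The 60 and 120 min steps have no downward margin. The 90 and 60 min steps share a category.

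**Step 2: infusions broken off.**

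- First infusion planned over 120 min, stopped at 20 min: the minimum is 20, so the subject is under 40 min.
- Three infusions of 120 min, then one at the 90 min step stopped at 35 min: the minimum is 35, so again under 40 min.
- For comparison, a completed 30 min infusion is also under 40 min.

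A grade 1 or 2 reaction works the other way, because the infusion may resume at half rate. Stopped at 30 min of 120, the remaining 90 min of infusion takes 90 × 2 = 180 min. The total is 30 + 180 = 210 min before any pause, which is in the category of 3 h or more.

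**Step 3: small timing slips.** Let q be the chance that an infusion at the 60 or 120 min step is recorded at least 1 min short, and k the number of infusions at that step, for a subject who has no infusion in a shorter category. With independent slips, the chance of moving one category shorter is 1 − (1 − q)^k. For q = 5% and k = 3 this is 1 − 0.95³ = 1 − 0.857 = 14%. The values of q are assumptions, shown as a range:

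| q (assumed) | k = 1 | k = 2 | k = 3 | k = 5 |
|---|---|---|---|---|
| 5% | 5% | 10% | 14% | 23% |
| 10% | 10% | 19% | 27% | 41% |
| 25% | 25% | 44% | 58% | 76% |

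The left-hand columns matter most. Under Protocol 9.1.1 a tolerated infusion at 120 or 60 min is followed by a shorter one. Several infusions at one of these steps arise mainly after a reaction or in the exceptional cases kept at 2 hours.

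**Step 4: limits between the steps.** The midpoints are (30 + 45)/2 = 37.5, (45 + 60)/2 = 52.5, (60 + 90)/2 = 75 and (90 + 120)/2 = 105 min. With these, 119 min stays with the 120 min step, 59 min stays with the 60 min step, and 60 and 90 min are told apart.

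**The case against.** The SAP files this variable under exposure, and a shortest recorded duration is literally what the label promises. Infusion time is not among the objectives or endpoints in SAP section 2.

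Reactions are not hidden either. SAP 10.2 tabulates infusion reactions, summarises time to the first one of grade 3 or higher, and lists both infusion reactions and AEs leading to discontinuation of MOR03087. Table 5 also gives the number of infusions with a modification and the average percentage of planned volume given.

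Both routes are narrow. The aborted-infusion route needs a stop early enough to fall in a shorter category than any completed infusion of that subject. It is normally one record per subject, because study drug then ends, and it presumes that the eCRF (not available here) records a stop time. The timing route does not touch anyone who goes on to a shorter category, and the limits are inclusive, so exactly 60 or 120 min is classed correctly.

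All of this stands, and it limits the importance of the point. It does not remove it: the other tables and listings let a reader trace a case, but they do not change the count in the shortest category.

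**Conclusion.** The point holds as a minor defect in a derived variable. With no completion condition, an infusion broken off early can place a subject in the same category as one who completed 30 min. The limits at 1 h and 2 h can move a subject whose shortest step was 60 or 120 min one category shorter. A minimum can only err towards shorter, so the direction is clear; the size is not known. The table above shows what would follow from assumed slip rates, not what will happen.

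Two stronger readings are tempting and are not supported.

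- A reader might infer that the trial will report a favourably biased conclusion on how short an infusion is feasible or tolerated. No such conclusion is planned in either document. The misreading arises only if this exposure variable is taken as a measure of tolerability.
- A reader might assume that half of all 60 and 120 min infusions are recorded short, so that 1 − 0.5^k = 75%, 88% or 94% of subjects with 2, 3 or 4 such infusions are misclassified. Nothing in the documents supports a rate of 50%, and the shortening scheme makes repeated infusions at a subject's shortest step uncommon when that step is 60 or 120 min.

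No endpoint, DLT count or MTD decision depends on this variable.

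**What to change.** In SAP Table 5:

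1. Derive the shortest category only from infusions in which the actual volume equals the planned volume. Table 5 already derives this percentage, including the rules for a blank volume. Where the percentage stays missing, completion is not established and the infusion should not enter the minimum.
2. Place the limits between the protocol steps, for example at 37.5, 52.5, 75 and 105 min, and keep the limit at 180 min so that prolonged infusions still have a category. Use the same limits in the per-infusion line.
3. Add one row for subjects with no completed infusion and one for the number of incompletely given infusions.

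Do not exclude every infusion marked as modified. That would also drop infusions that were prolonged but given in full.

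The cost is one derivation and a few lines of SAP text, using data already collected. The downside is small: subjects with no completed infusion have no category, and the table gains rows.
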